## 7.5. Preparation/Handling/Storage/Accountability

A description of the methods and materials required for preparation of GSK2398852, Zr-GSK2398852, and GSK2315698 will be detailed in a Study Specific Technical Agreement/Memo (TTS) or Pharmacy Manual which will be accompanied by a Quality Agreement.

1. The investigator or designee must confirm appropriate temperature conditions have been maintained during transit for all study treatment received and any discrepancies are reported and resolved before use of the study treatment.
  2. Only subjects enrolled in the study may receive study treatment and only authorized site staff may supply or administer study treatment. All study treatments must be stored in a secure, environmentally controlled, and monitored (manual or automated) area in accordance with the labeled storage conditions with access limited to the investigator and authorized site staff.
  3. The investigator, institution, or the head of the medical institution (where applicable) is responsible for study treatment accountability, reconciliation, and record maintenance (i.e., receipt, reconciliation, and final disposition records).
  4. Further guidance and information for the final disposition of unused study treatment are provided in the Study Reference Manual.
- Under normal conditions of handling and administration, study treatment is not expected to pose significant safety risks to site staff. Take adequate precautions to avoid direct eye or skin contact and the generation of aerosols or mists. In the case of unintentional occupational exposure notify the monitor, Medical Monitor and/or GSK study contact.
  - A Material Safety Data Sheet (MSDS)/equivalent document describing occupational hazards and recommended handling precautions either will be provided to the investigator, where this is required by local laws, or is available upon request from GSK.

## 7.6. Treatment Compliance

When subjects are dosed at the site, they will receive study treatment directly from the investigator or designee, under medical supervision. The date and time of each dose administered in the clinic will be recorded in the source documents. The dose of study treatments and study subject identification will be confirmed at the time of dosing by a member of the study site staff other than the person administering the study treatment.

## 7.7. Concomitant Therapy

Any medication or vaccine (including over-the-counter or prescription medicines, vitamins, and/or herbal supplements) that the subject is receiving at the time of enrollment or receives during the study must be recorded along with:

- reason for use
- dates of administration including start and end dates
- dosage information including dose and frequency

Subjects usual medication can be continued during this study with the exception of those listed in Section 7.7.2.

New chronic concomitant medication should be discussed with the GSK Medical Monitor.

The Medical Monitor should be contacted if there are any questions regarding concomitant or prior therapy.

### 7.7.1. Pre-medication prior to unlabelled anti-SAP mAb

A non-selective antihistamine (e.g. chlorphenamine 10-20 mg) and hydrocortisone 100 mg (or equivalent) should be given prior to each infusion of unlabelled anti-SAP mAb. Additional administrations of either or both medications are permitted at discretion of Investigator or designee if symptoms require this.

Given that the infusion of Zr-GSK2388852 will commence during or shortly after the infusion of the unlabelled anti-SAP mAb infusion, administration of a separate premedication schedule is not required before the radiolabelled mAb infusion commences.

### 7.7.2. Prohibited Medications and Non-Drug Therapies

The following restrictions apply from pre-screening up to the final visit.

**Table 9 Restricted Medications**

Medication	Pre-screen restriction
Tafamidis, diflunisal, tauroursodeoxycholic acid (TUDCA)	Initiation of, or change of dose, within 28 days
Green tea extract	Initiation of, or change of dose, within 28 days
Silencing therapies (e.g. small interfering ribonucleic acid [siRNA]) for ATTR protein synthesis	3 months
Disease-modifying drug for any type of autoimmune disease, including but not restricted to, methotrexate, cyclophosphamide, or anti-cytokine antibodies (e.g. anti tumor necrosis factor (TNF)- $\alpha$ monoclonal antibody)	At any time
Antibody therapy for amyloidosis treatment	At any time

Where these are deemed to be clinically necessary by the treating physician the individual subject will be withdrawn from the study.

## **7.8. Treatment after the End of the Study**

The investigator is responsible for ensuring that consideration has been given to the post-study care of the subject's medical condition, whether or not GSK is providing specific post-study treatment.

Given the lack of information about the safety and efficacy of Anti-SAP treatment in ATTR-CM, treatment will not be provided after the end of the study. This may be reviewed once more information is available.

## **8. DISCONTINUATION CRITERIA**

### **8.1. Discontinuation of Study Treatment**

#### **8.1.1. Discontinuation for failure to deplete plasma SAP levels with IV CPHPC**

Subjects will be withdrawn from the study if they are unable to deplete plasma SAP levels to target (Section 5.4 and Section 5.5).

#### **8.1.2. Adverse Event Discontinuation Criteria**

Subjects with any adverse event(s) (e.g. skin rash) that have arisen during the 1st dosing session and is potentially attributable to administration of any component of Anti-SAP treatment or Zr-GSK2398852, and that has not completely resolved by the time the 2nd dosing session is expected to commence, will be withdrawn from the study.

### 8.1.3. Renal Function Discontinuation Criteria

Subjects will not receive anti-SAP mAb if

- The eGFR calculated by the MDRD equation has reduced to  $<40$  mL/min/1.73m^2 after Screening,
- or
- There has been a reduction in eGFR from baseline by  $>50\%$ .

If the eGFR falls to between 40 – 50 during the trial, the subject can continue participation at the investigator/designee's discretion.

Dose adjustment of IV and / or SC CPHPC may be necessary for subjects with reduced eGFR at baseline, before administration of anti-SAP mAb in the 2nd dosing session, or at any time during the study; refer to Section 7.2.1 and Table 8 for CPHPC renal dosing regimen.

### 8.1.4. Cardiovascular Safety Discontinuation Criteria

#### 8.1.4.1. Individual subject cardiovascular stopping criteria

A subject who meets any criterion below will be withdrawn from the study.

1. Acute coronary syndrome or myocardial infarction
2. Decompensated heart failure, or worsening heart failure that is refractory to medical management
3. **New** & symptomatic bradyarrhythmia
4. **New** sustained monomorphic VT ( $\geq 120$  beats/min for  $\geq 30$  seconds), or development of new rapid polymorphic VT, or new ventricular fibrillation (VF)
5. Symptomatic myocarditis
6. Requirement for LVAD implantation, or consideration of urgent cardiac transplantation during the Study
7. Development of any rhythm disorder during the study which requires either prophylaxis or treatment with a permanent cardiac pacemaker, or ICD

[figure not shown]
### 8.1.5. Liver Chemistry Stopping Criteria

**Liver chemistry stopping and increased monitoring criteria** have been designed to assure subject safety and evaluate liver event etiology.

Discontinuation of study treatment for abnormal liver tests is required when:

- a subject meets one of the conditions outlined in the algorithm ([Figure 5](#))
- when in the presence of abnormal liver chemistries not meeting protocol-specified stopping rules, the investigator believes study treatment discontinuation is in the best interest of the subject.

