**Overall Design:**

This is an open-label non-randomised Zr-GSK2398852 PET imaging study in clinically stable patients with either wild type or inherited ATTR-CM. Subjects will participate in up to two dosing sessions.

Each dosing session will include:

- Administration of anti-SAP treatment consisting of:
  - CPHPC administered via intravenous (IV) infusion for at least 48 hours, followed by
  - Unlabelled anti-SAP mAb together with Zr-GSK2398852 via two separate intravenous infusions, and
  - CPHPC administered via subcutaneous (SC) injections for at least 9 days.
- Up to three PET scans at varying intervals after Zr-GSK2398852 administration.
- An inpatient stay of up to 11 days, followed by an additional week of outpatient cardiac monitoring.

At a single suitable time point, depending on technical and logistic aspects, the subject will undergo one additional PET scan with the administration of Carbon-11 Pittsburgh Compound B (PiB), a tracer known to bind to amyloid, for the characterization of the regional amyloid burden in the heart, and up to two further PET scans with the administration of Oxygen-15 labelled water (WAT) for the characterization of the regional blood flow in the heart.

This study has an adaptive study design in order to identify the conditions and dose of anti-SAP mAb which provide optimal assessment of cardiac update. As the name suggests, systemic amyloidosis is associated with amyloid deposits in multiple organs. The delivery of monoclonal antibodies to individual organs depends on the blood flow and nature of the endothelium. Because the amount of tracer Zr-GSK2398852 is small relative to total amyloid load, if given alone it would distribute to the best-perfused organs with discontinuous endothelia. For this reason, the radiolabelled tracer will be co-administered with unlabelled anti-SAP mAb so that distribution will better reflect the situation when therapeutic doses are administered.

During each dosing session, subjects will receive a TMD of anti-SAP mAb ≤500 mg. The dose will vary between subjects and dosing sessions, and will be contingent on both the PET imaging and Zr-GSK2398852 PK findings from the 1st dosing session, or the findings from previous subjects.

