**Footnotes:**

1. Screening to take place within 35 days of start of Anti-SAP treatment.
2. Baseline will be any time after eligibility confirmed and before Anti-SAP treatment starts. Procedures may be done on different days.
3. Full examination at screening only, brief examination at all other time-points.
4. Out-patient cardiac recording (see Section 3.4.1.3): Baseline for approximately 1 week, and from Day 11 for approximately 1 week after discharge.
5. See Other Screening Tests in [Appendix 2](#)
6. Requires rapid turnaround. See Section 5.5 Plasma SAP Target
7. See Section 5.6 for timing of administration of unlabelled anti-SAP mAb and Zr-GSK2398852.
8. Dosing Session 2 only, if logistically feasible. Can be done any day/time prior to anti-SAP mAb.
9. Exact timing in relation to end of Zr-GSK2398852 infusion will change based on emerging data. See Section 5.3.1.
10. CPHPC IV infusion for a minimum of approximately 48 hours. To be stopped prior to mAb infusion.
11. First SC dose to be administered approximately 5 hours after end of IV CPHPC infusion.
12. Administered three times daily. See Section 7.1 and Section 7.2
13. In triplicate.
14. See [Table 5](#)
15. Female Subjects Only.
16. The last visit of the final study session will be considered the final follow-up visit. This may be conducted in-person, or by “virtual visit”.
17. See [Table 4](#) for sampling times and windows.
18. See [Table 3](#) for allowable time/visit windows.
19. Third Zr PET-CT to be done in first two subjects who complete Part A, only. Subsequent subjects to undergo only two Zr PET-CT scans.
20. From Day 6 onward, at investigator discretion, inpatient cardiac monitoring can be performed via remote cardiac telemetry device (e.g. BodyGuardian device)
21. If logistically possible.

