## **5.12. Scientific Rationale for Study Design**

### **5.12.1. Justification for the administration of CPHPC & unlabelled anti-SAP mAb**

#### **5.12.1.1. CPHPC**

Pharmacologically, IV CPHPC is a highly predictable drug as demonstrated in FIH study (SAP115570) where all systemic amyloidosis subjects attained plasma SAP depletion below the specified target level.

In the FIH study (SAP115570), the standard dosing regimen of CPHPC consisted of an IV infusion of 20 mg/hour for 72 hours prior to anti-SAP mAb administration. This regimen was both effective and consistently predictable in depleting circulating SAP to <2 mg/L (Hycult ELISA assay). Since there is no precedent for the present treatment, this empirical target SAP concentration was adopted on the basis of evaluation of the formation of potentially harmful (i.e. high titres of) circulating immune complexes. Safety evaluation in the FIH study did not identify any signals suggestive of adverse effects from residual plasma SAP, such as clinical manifestations of systemic/organ vasculitis.

CPHPC is predominantly cleared from the plasma by the kidneys and excreted in the urine. CPHPC doses will therefore be adjusted (see Section 7.2.1, Table 8) based on individual renal function as measured by eGFR using the existing pharmacokinetics/pharmacodynamics (PK/PD) model of CPHPC [Sahota 2015].

Subjects in the FIH study achieved the target plasma SAP by 48 hours CPHPC IV treatment and therefore the duration of the initial CPHPC infusion prior to administration of anti-SAP mAb has been shortened in this study. On retrospective analysis most, but not all, subjects in the FIH study had achieved the target plasma SAP depletion by 24 hours CPHPC (IV) with further depletion to 48 hours.

Subjects with overall low amyloid load, such as ATTR-CM patients in this study, are likely to deplete their plasma SAP level to target within 48 hours of administration of IV CPHPC. The first plasma SAP concentration will be checked after 24 hours of administration of IV CPHPC to confirm whether the anti-SAP mAb and Zr-GSK2398852 can be administered at approximately 48 hours after initiation of IV CPHPC.

The total duration of administration of maintenance SC CPHPC in this study will be 8 days (i.e. last dose per session on Day 11), and is in line with the schedule of administration in the Phase 2 study (201464).

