## 7. TREATMENTS

Study treatment is defined as any investigational treatments intended to be administered to a study subject according to the study protocol.

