### 7.1. Treatments Administered

Study Treatment Name:	GSK2315698 (CPHPC)	GSK2398852 (unlabelled anti-SAP mAb)	$^{89}\text{Zr}$ -GSK2398852 ( $^{89}\text{Zr}$ -Df-labelled anti-SAP mAb)
Dosage formulation:	GSK2315698 Solution for Subcutaneous Injection or Intravenous Infusion, 200 mg/mL	GSK2398852 Concentrate for Solution for Infusion, 100 mg/mL	Solution containing 10 mg $^{89}\text{Zr}$ -GSK2398852 for Infusion, 10 mg/10mL or 10 mg/20mL

Study Treatment Name:	GSK2315698 (CPHPC)	GSK2398852 (unlabelled anti-SAP mAb)	Zr-GSK2398852 (Zr-Df-labelled anti-SAP mAb)
Unit dose strength(s)/ Dosage level(s):	200 mg/mL provided as 2 mL solution per vial Dosage levels: variable dependent on renal function	100 mg/mL provided as 1 mL solution per vial.  Variable total mass doses of anti-SAP mAb not exceeding 500 mg per dosing session	37 MBq  Zr-GSK2398852 associated with a mass of 10 mg GSK2398852
Route of Administration	Intravenous infusion usually for approximately 48 hours but up to 72 hours  Subcutaneous injection up to 3x daily for up to 8 days after unlabelled anti-SAP mAb dose per dosing session	Intravenous infusion of variable duration.	Refer to Table 6
Dosing instructions:	Study medication will be diluted in 0.9% w/v sodium chloride and administered by intravenous infusion by study personnel following specified regimens and by subcutaneous injection by study personnel in in-patient setting	Study medication will be diluted in 0.9% w/v sodium chloride and administered by intravenous infusion by study personnel following specified regimens	To be administered via separate intravenous cannula.  Refer to Table 6 See local Standard operating procedure (SOP) to protect from ionising radiation
Packaging and Labelling	Study Treatment will be provided in Type 1 clear glass vials sealed with grey polymer coated rubber stoppers that meet extractable criteria for sterile dosage forms. A silver aluminium overseal is placed over each vial and crimped. Each vial will be labelled as required per country requirement.	Study Treatment will be provided in glass vials. Each vial will be labelled as required per country requirement.	Study Treatment will be provided in glass vials. Each vial will be labelled as required per country requirement.

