### Phase I liver chemistry stopping criteria and required follow up assessments

Liver Chemistry Stopping Criteria – Liver Stopping Event	
ALT-absolute	
ALT<math>\geq</math>3xULN
 
If ALT<math>\geq</math>3xULN AND bilirubin <math>\geq</math> 2xULN (>35% direct bilirubin) OR INR >1.5, Report as an SAE.
 
See additional Actions and Follow Up Assessments listed below

Required Actions and Follow up Assessments	
Actions	Follow Up Assessments

 
• Immediately discontinue study treatment
 
• Report the event to GSK within 24 hours
 
• Complete the liver event CRF, and complete an SAE data collection tool if the event also meets the criteria for an SAE
 
• Perform liver chemistry event follow up assessments
 
• Monitor the subject until liver chemistries resolve, stabilise, or return to within baseline (see MONITORING below)
 
• Do not restart/rechallenge subject with study treatment unless allowed per protocol and GSK Medical Governance approval is granted (see below). If restart/rechallenge not allowed per protocol or not granted, permanently discontinue study treatment and continue subject in the study for any protocol specified follow up assessments
 
 
MONITORING:
 
If ALT<math>\geq</math>3xULN AND bilirubin <math>\geq</math> 2xULN or INR >1.5:
 
 
• Repeat liver chemistries (include ALT, AST,
 
	
 
• Viral hepatitis serology
 
• Obtain INR and recheck with each liver chemistry assessment until the transaminases values show downward trend
 
• Obtain blood sample for pharmacokinetic (PK) analysis, obtained within 5 days of last dose of CPHPC or anti-SAP mAb.
 
• Serum creatine phosphokinase (CPK) and lactate dehydrogenase (LDH).
 
• Fractionate bilirubin, if total bilirubin<math>\geq</math>2xULN
 
• Obtain complete blood count with differential to assess eosinophilia
 
• Record the appearance or worsening of clinical symptoms of liver injury, or hypersensitivity, on the AE case report form (CRF)
 
• Record use of concomitant medications on the concomitant medications CRF page including
 

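### Read literally after the Day 3 antibody, the liver stopping rule also ends the SC CPHPC that Sections 5.4 and 8.2 ask sites to continue

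*Protocol*

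**What the plan says.** **Scope of the term.** Protocol Section 7: "Study treatment is defined as any investigational treatments intended to be administered to a study subject according to the study protocol". The Section 7.1 table lists three such treatments. CPHPC is one of them, and its entry includes the course after the antibody: "Subcutaneous injection up to 3x daily for up to 8 days after unlabelled anti-SAP mAb dose per dosing session".

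**Liver rule.** Section 8.1.5: "Discontinuation of study treatment for abnormal liver tests is required when", followed by the triggers, the first of which refers to Figure 5. Appendix 6 sets the threshold at ALT ≥3xULN, tells the site to stop study treatment at once and asks for a report within 24 hours. Where restart is not allowed by the protocol, the site must "permanently discontinue study treatment and continue" the subject in the study for follow-up. Section 8.1.9.1 does not allow restart after a liver event. Appendix 6 also asks for a PK sample "obtained within 5 days of last dose of CPHPC or anti-SAP mAb".

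**QTc rule.** Section 8.1.6 withdraws the subject from study treatment at QTc ≥530 msec or a rise of more than 60 msec. It does not say that this is immediate, and no restart ban covers it.

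**CPHPC after the antibody.** Section 5.4, in bold, wants SC CPHPC given after the antibody so that circulating SAP stays low and large amounts of immune complex do not form. It extends this to subjects who withdraw from the study. Section 8.2, also in bold, asks for the SC course to be completed where possible.

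**Timing.** The first SC dose falls on Day 3 (SoA footnote 11: "First SC dose to be administered approximately 5 hours after end of IV CPHPC infusion"). Section 5.12.1.1 puts the last dose of each session on Day 11.

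**The concern.** The two sets of instructions collide in one situation: a liver trigger after the antibody has been given. The site must stop study treatment at once and for good, yet it has also been told that CPHPC has to follow the antibody. Following the liver rule withdraws the drug that keeps SAP low while antibody is still present, which is the outcome Section 5.4 warns against. The restart ban would then prevent CPHPC from being resumed in that session. Following Section 5.4 instead departs from a mandatory stopping rule, in a protocol whose Section 9 allows no waivers.

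The stake is subject safety and clear conduct at the site. No endpoint, sample size or analysis in the SAP depends on it.

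**Working it through.** There is no design figure to reproduce. The check compares texts and then works out the timing.

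**1. What is left to stop after the antibody.** IV CPHPC ends before the antibody starts (Section 5.4), and each session has one antibody administration. After the Day 3 infusions, CPHPC is the only study treatment remaining in that session. In Part B, or in the second session of Part A, no later antibody dose is planned (Table 1). A stop there either means stopping CPHPC or has nothing to act on.

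**2. How each stopping rule treats CPHPC.**

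| Rule | What stops | What it says about CPHPC |
|---|---|---|
| Renal, 8.1.3 | Antibody | Dose adjustment addressed |
| Cardiovascular, 8.1.4.1 | Participation in the study | Covered directly by 5.4 |
| Dermatological, 8.1.7.1 | Further sessions | Oedema item: continue by IV to Day 11 |
| Grade 4 rash, Table 12 with 12.7.3 | Study treatment, explained as no further antibody | Continue to Day 11 where feasible |
| Liver, 8.1.5, Appendix 6, 8.1.9.1 | Study treatment, immediately and permanently | Nothing visible |
| QTc, 8.1.6 | Study treatment | Nothing |

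The Grade 4 rash row matters most. Table 12 uses the same term, and 12.7.3 then explains that it does not include CPHPC. The liver and QTc rules use the term without that explanation.

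**3. Time left when a trigger can occur.** Whole days of SC CPHPC left after trigger day d are 11 − d, plus any doses still due on day d. The SoA places post-antibody chemistry on Days 5, 7, 11 and 26, and ECGs from the end of the Day 3 infusion through Day 11.

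- Liver rule: Day 5, 11 − 5 = 6; Day 7, 11 − 7 = 4; Day 11, 0.
- QTc rule only: Day 3, 11 − 3 = 8; Day 4, 11 − 4 = 7.

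At three doses a day, a Day 5 liver trigger forgoes up to 6 × 3 = 18 doses. I give no share of the course, because its length is stated in two ways: 8 days in 5.12.1.1 and 7.1, but in the synopsis "CPHPC administered via subcutaneous (SC) injections for at least 9 days". Both are compatible with an end on Day 11 (Days 3 to 11 inclusive are 9 calendar days, and Day 11 is 8 days after Day 3).

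**4. Antibody still present (context only).** Section 5.13.1 gives a half-life of about 15 hours at 80 mg and expects slower clearance at higher doses. Under single-exponential decay, the fraction left is 0.5^(t/half-life). At 48 h with 15 h this is 0.5^3.2 = 10.9%. The 30 h and 60 h columns are my assumptions.

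| Time after infusion | 15 h (stated) | 30 h (assumed) | 60 h (assumed) |
|---|---|---|---|
| 24 h, Day 4 (QTc only) | 33.0% | 57.4% | 75.8% |
| 48 h, Day 5 (first liver test) | 10.9% | 33.0% | 57.4% |
| 96 h, Day 7 | 1.2% | 10.9% | 33.0% |

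**5. Can sponsor contact close the gap in time?** The liver stop is immediate, while the report may take up to 24 hours. SC doses are about 8 hours apart (Table 8), so up to 24 / 8 = 3 could be missed first.

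**The case against.** The best reply is that the protocol already answers the question.

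- Section 5.4 keeps CPHPC going even on withdrawal from the study, which is a larger step than stopping treatment, so the smaller step is covered by implication.
- Section 8.2 makes its request after noting that stopping treatment need not mean leaving the study, so it is not confined to study withdrawal.
- The oedema item and the Grade 4 rash text point the same way.
- The Appendix 6 mention of CPHPC only times a blood sample; it does not say which drug to stop.
- The setting is well controlled: up to six subjects, inpatient to Day 11, doses given by staff, immediate safety concerns taken to the sponsor (Section 9).

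Most of this stands, and it settles what the authors intended. It does not repair the liver text. That rule is mandatory, immediate and permanent, uses a term defined to include CPHPC, and describes a subject who stays in the study, a state that Section 5.4 does not name. Section 8.2 is qualified and cannot override a required stop.

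Two further points stand in full. Figure 5 is not visible and may hold an exception; its absence here is not a fault of the plan. And the documents give no hepatic or QT data for CPHPC, so continuing it after a liver event should not be unconditional.

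**Conclusion.** The point holds for the liver rule: followed as written after the antibody, it removes a safeguard that the protocol puts in bold elsewhere. At the earliest scheduled trigger, Day 5, this costs 6 further whole days of SC CPHPC, with about 11% of the antibody left at the stated 15-hour half-life and more if clearance is slower. It rests on the visible text, on single-exponential decay, and on Figure 5 containing no exception. Before the antibody is given there is no conflict.

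A reader might go further in three ways that the documents do not support.

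- *That nothing indicates which instruction prevails.* Sections 5.4, 8.2, 8.1.7.1 and 12.7.3 all favour continuing CPHPC.
- *That the QTc rule is equally serious.* It has the same wording gap, but it is not stated as immediate and carries no restart ban, so a site can more easily follow Section 5.4. The larger Day 3 and Day 4 figures belong to this milder case only.
- *That the antibody fractions measure harm.* Immune-complex risk also depends on how fast SAP returns once CPHPC stops, and no such rate is given. Section 5.9 says only that 4 weeks are allowed for return to baseline. The size of the risk is unknown.

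**What to change.** In Section 8.1.5 and Appendix 6 and, for consistency, in Section 8.1.6, state that:

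- the stop applies to any ongoing or further unlabelled anti-SAP mAb and 89Zr-GSK2398852, and to further dosing sessions;
- once antibody has been given, CPHPC continues to Day 11 on the terms already used in 12.7.3, unless the investigator and Medical Monitor judge that the hepatic or QT risk outweighs the immune-complex risk.

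In Section 8.1.9.1, state that completing that CPHPC course is not a restart. Check Figure 5 and align it if needed.

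The cost is one or two sentences in each rule and one in 8.1.9.1, with no new procedure, visit or subject. The downside is some continued CPHPC exposure after a liver or QTc event, which the Medical Monitor exception limits.
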